### **8.3.5 ADVERSE EVENT REPORTING**

The investigator must record reportable adverse events to the DSMC and IRB according to timetable for reporting specified in sections 8.3.6 and 8.3.7.

---

### **8.3.6 UNANTICIPATED ADVERSE DEVICE EFFECTS REPORTING**

The Sponsor-Investigator must notify the reviewing IRB and all participating PIs in a UADE safety report of potential serious risks as soon as possible, but in no case later than 10 working days after the Sponsor-Investigator determines that the information qualifies for reporting. The reviewing IRB serves as a proxy to the FDA and will make recommendations whether the UADE should be submitted to the FDA. Thereafter, the Sponsor shall submit such additional reports concerning the effect as the reviewing IRB or FDA requests (21 CFR 812.150(a)(1)).

The Sponsor-Investigator who determines a UADE presents an unreasonable risk to participants shall terminate all investigations or parts of investigations presenting that risk as soon as possible. Termination shall occur not later than 5 working days after the Sponsor makes this determination and not later than 15 working days after the Sponsor first received notice of the effect (21 CFR 812.46(b)(2)).

All UADEs will be followed until satisfactory resolution or until the Sponsor-Investigator or site PI deems the event to be chronic or the adherence to be stable. Other supporting documentation of the event may be requested by the Sponsor-Investigator and should be provided as soon as possible.

All UADEs will be reported using the FDA 3500A Mandatory MedWatch report form unless funding sponsor or drug manufacturer requires use of proprietary form. UADE form can be found at:

<http://www.fda.gov/downloads/AboutFDA/ReportsManualsForms/Forms/UCM048334.pdf>

To submit a UADE, email as follows within 24 hours of becoming aware of the event:

To: [contact]

[contact]

[contact]

Subject: 20-1684 UADE Report Form

Attach: FDA 3500A form completed and signed by an Investigator

### **Follow-up of unresolved unanticipated adverse device effects**

Any UADEs that are unresolved at the time of the initial report submission should be followed up by the Investigator for as long as medically indicated, and an updated UADE report submitted at the time new information regarding the event becomes available.

---

## **8.3.7 REPORTING OF PREGNANCY**

Pregnant patients will not be enrolled in the study. Pregnancy status for female study candidate will be checked via a pregnancy test. A pregnancy test will be given at the treatment simulation (Day 1), which is part of the standard clinical care.

## **8.4 UNANTICIPATED PROBLEMS**

---

### **8.4.1 DEFINITION OF UNANTICIPATED PROBLEMS (UAP)**

The Office of Human Research Protection (OHRP) considers unanticipated problems involving risks to participants or others to include, in general, any incident, experience, or outcome that meets **all** of the following criteria:

- Unexpected in terms of nature, severity, or frequency given (a) the research procedures that are described in the protocol-related documents, such as the IRB-approved research protocol and informed consent document; and (b) the characteristics of the participant population being studied;
- Related or possibly related to participation in the research (“possibly related” means there is a reasonable possibility that the incident, experience, or outcome may have been caused by the procedures involved in the research); and
- Suggests that the research places participants or others at a greater risk of harm (including physical, psychological, economic, or social harm) than was previously known or recognized.

This study will use the OHRP definition of UAP.

### 8.4.2 REPORTING OF UNANTICIPATED PROBLEMS

Incidents or events that meet the OHRP criteria for UAPs require the creation and completion of a UAP report. It is the Sponsor-Investigator or Site PI's responsibility to report UAPs to their IRB. The Lead PI is responsible for reporting the UAP to the IRB and the UCCC DSMC. The UAP report will include the following information:

- Protocol-identifying information: protocol title and number, PI's name, and the IRB project number;
- A detailed description of the event, incident, experience, or outcome;
- An explanation of the basis for determining that the event, incident, experience, or outcome represents a UAP;
- A description of any changes to the protocol or other corrective actions that have been taken or are proposed in response to the UAP.

## 9 STATISTICAL CONSIDERATIONS

### 9.1 STATISTICAL HYPOTHESES

- Primary Efficacy Endpoint:  
The primary endpoint of this study is to evaluate the change in objective image quality metrics in CBCT images acquired with the 2D grid, when compared to CBCT images without the 2D grid. We will place multiple ROIs in each CBCT scan, and calculate absolute CT number error, artifact amplitude, and contrast to noise ratio (CNR). We will evaluate the statistical significance of the differences of these metrics between research CBCT and standard clinical CBCT scans. We hypothesize that CBCT scan with 2D grid will provide significantly lower CT number errors and artifact amplitudes when compared to standard clinical CBCT scans. We also hypothesize that CBCT scans with 2D grid will provide equivalent or better CNR than standard clinical CBCT scans.
- Secondary Efficacy Endpoint(s):
  - 1) We hypothesize that the accuracy of software tools can also be improved in auto-delineation of tissues in CBCT scans. In this case, we will use manual delineations from the observers as the gold standard and measure the similarity of software generated and observer generated delineations by using the CI and HD metrics.

- Tertiary Efficacy Endpoint(s):
  - 1) Assessment of radiomics feature extraction accuracy: We hypothesize that image intensity and texture (radiomics) features are more consistent in higher quality CBCT images. The gold standard consistency of radiomics features is MDCT scans. Thus, we will evaluate the correlation of radiomics features in CBCT scans and MDCT scans, by using the CCC metric. Higher correlation of radiomics features between CBCT and MDCT scans will yield higher CCC values.
  - 2) Assessment of image quality rankings by observers, evaluation of quantitative image quality metrics, and evaluation of dose calculation accuracy. Metrics obtained in each study will be evaluated comparatively. The statistical significance of differences in quality metrics extracted from research and standard clinical CBCT scans will be evaluated.
  - 3) Determine the consistency of organ/tissue delineations across different observers, when using CBCT image sets with better image quality. We will calculate intra-class correlation coefficient (ICC) on CI and HD metrics to measure the effect of standard clinical CBCT and 2D Grid CBCT on organ delineation consistency.

We hypothesize that organ/tissue delineations performed by observers will be more accurate, or more consistent, if tissue visualization is better in CBCT scans. However, gold standard tissue delineations do not exist in CBCT scans. Therefore, we will compare the consistency, or similarity, of delineations performed by multiple observers. If tissue visualization is improved in a CBCT scan, we expect higher inter-observer similarity of delineations.

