## 9.4 STATISTICAL ANALYSES

### 9.4.1 GENERAL APPROACH

**Study #1 (Primary objective):** Improvement in tissue visualization and quantitative accuracy will be evaluated comparatively between the CBCT scans acquired with and without the 2D grid. Objective image metrics will be employed to quantify tissue visualization and quantitative accuracy. Three image quality metrics will be extracted from each CBCT scan; absolute CT number error, image artifact amplitude, and contrast to noise ratio (CNR). To calculate CT number errors and artifact amplitude, multiple ROIs will be placed primarily in the soft tissue and adipose sections of the imaged anatomy in coregistered CBCT and simulation CT images. CT number error is defined as the absolute difference in mean HU values between the CBCT and the gold standard CT images of a given ROI. Artifact amplitude is defined as the difference between the maximum and minimum value of CT number errors extracted from ROIs in a given CBCT scan. For CNR calculations paired ROIs will be placed in each imaged volume, such that one of the ROIs in the pair will be placed in soft tissue, and the other will be placed in adipose tissue in proximity of the first ROI. CNR is calculated by using the following:

$$CNR = \frac{|HU_{soft} - HU_{adipose}|}{(\sigma_{soft} + \sigma_{adipose})/2}$$

Where  $HU_{soft}$  and  $HU_{adipose}$  are the mean HU values of soft tissue and adipose tissue ROI pairs.  $\sigma_{soft}$  and  $\sigma_{adipose}$  are the HU standard deviation of soft tissue and adipose tissue ROI pairs. These metrics serve as surrogates that quantify tissue visualization. A statistically significant improvement in these metrics when compared to metrics extracted from standard clinical CBCT scans would indicate that tissue visualization and quantitative accuracy would be potentially improved by CBCT scans with 2D grid.

**Study #2 (Secondary Objective), evaluate the consistency of organ delineation by automated software tools:** Evaluations in study 2 will be similar as those in study 1. The exception is that the pairwise comparisons will consist of comparing the automated software delineation to delineations for each of the four observers. This will allow us to evaluate how consistent the automated delineation is with human delineations, and whether a given imaging modality results in a more consistent automated delineation.

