Analysis of radiomics feature extraction accuracy: In each image set, we will extract series of radiomics features, such as HU value statistics (e.g. mean, variance, and kurtosis), and texture features, such as gray-level co-occurrence matrix, wavelets, local entropy. Accuracy and repeatability of radiomics features in CBCT (both standard and 2D grid CBCT) and gold standard helical CT will be evaluated using Lin's concordance correlation coefficient (CCC) as in Zhao's work [35]. Statistical analysis details of other potential exploratory studies, such as qualitative and quantitative image quality evaluations, and CBCT-based dose calculations will be determined on an ad hoc basis.

The analysis of TrueBeam (Groups 1-3) and Proteus (Group 4) CBCT images. An image quality difference is expected between TrueBeam and Proteus CBCT due to differences in system design (e.g. TrueBeam has bow tie filter, whereas Proteus does not have one), and image reconstruction chain. Therefore, in the primary analysis, we will analyze the data from patient Groups 1-3 (TrueBeam) and Group 4 (Proteus) separately. This way, we will eliminate potential, system-specific image quality bias. In a subgroup analysis, we will investigate the differences in the study results of Groups 2 and 4 (i.e. prostate cancer patients scanned with TrueBeam and Proteus, respectively).

---

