#### **9.4.2 ANALYSIS OF THE PRIMARY EFFICACY ENDPOINT(S)**

Our primary analysis will evaluate the tissue visualization and quantitative accuracy of CBCT scans with 2D grid, as measured by objective image quality metrics. These metrics, namely absolute CT number error, artifact amplitude, and CNR, will be extracted from research CBCT

and standard clinical CBCT pairs of each study participant. In each CBCT image set, each metric will be measured from multiple ROIs, and their respective average values will be calculated. Subsequently, these values will be log transformed (natural logarithms) for the validity of normality. The Linear Mixed Effects model will be used to evaluate the differences in image quality metrics among CBCT types, while adjusting the random patients effect. The lower and upper limits of the 95% confidence interval will be calculated for each image quality metric and for each CBCT type. Image quality metrics of research CBCT scans and standard clinical CBCT scans will be compared in a pairwise fashion for the statistical significance of the differences between the two CBCT types. In a subgroup analysis, image quality metrics will be stratified into anatomical region groups and patient size groups to assess the effect of anatomical region and patient size on the image quality differences between the two CBCT types.

---

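### The plan hypothesises that CNR with the 2D grid is at least as good as standard, but provides only a test for a difference, which cannot show this

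*Combined protocol and SAP*

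**What the plan says.** Section 9.1 sets two kinds of primary hypothesis. For two metrics it is superiority: "We hypothesize that CBCT scan with 2D grid will provide significantly lower CT number errors and artifact amplitudes" relative to standard clinical scans. For CNR it is weaker: "We also hypothesize that CBCT scans with 2D grid will provide equivalent or better CNR than standard clinical CBCT scans".

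Section 9.4.2 applies one analysis to all three metrics. ROI values are averaged within each scan, log transformed and entered in a linear mixed model with a random patient effect. The two scan types are then "compared in a pairwise fashion for the statistical significance of the differences between the two CBCT types". The 95% confidence limits are specified for each metric and each CBCT type. No interval is specified for the difference or ratio between types.

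Section 9.4.1 (Study #1) comments on all three metrics together: "A statistically significant improvement in these metrics when compared to metrics extracted from standard clinical CBCT scans would indicate" a potential improvement in visualization and quantitative accuracy. The endpoint table in Section 3 likewise expects all three to improve.

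On cohorts, Section 9.4.1 says: "in the primary analysis, we will analyze the data from patient Groups 1-3 (TrueBeam) and Group 4 (Proteus) separately". Section 9.2 attaches the sample size for the primary hypothesis to the 32 participants of Groups 1-3. Group 4 has 10 participants (Section 4.1).

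No section gives a CNR margin, a significance level for the primary tests, or a statement of which metrics and which cohort decide the primary conclusion.

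**The concern.** A claim that one scan is at least as good as another needs evidence that any loss is smaller than some stated amount. A test of the null hypothesis of no difference does not supply it. If it is significant in favour of the grid, it shows superiority, which is more than was hypothesised. If it is non-significant, it shows neither equality nor loss. The outcome that Section 9.1 explicitly allows for, an unchanged CNR, therefore has no route to a positive finding.

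The per-type intervals do not fill the gap. Each describes the mean CNR of one scan type and carries between-patient variation that the paired design is meant to remove. What is needed is the interval for the within-patient ratio.

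With CNR unchanged or slightly changed, the report would have no planned way to say whether the CNR hypothesis was met. Sections 3 and 9.4.1 would lead a reader to expect improvement, while Section 9.1 would be content with equality.

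**Working it through.** **Plan's own figure.** There is none for CNR. The calculation in Section 9.2 concerns an intraclass correlation for observer delineations, now exploratory (Section 9.4.7). Only its cohort size is used here.

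**Inputs from the documents.** n = 32 for Groups 1-3 (Section 9.2); n = 10 for Group 4 (Section 4.1); natural-log scale and pairing within patient (Section 9.4.2).

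**Assumptions.** Two-sided 0.05 for the primary tests, in line with the 95% intervals (a 0.05 level is stated only for the exploratory ICC comparison in Section 9.4.7). SD of the paired log CNR ratio 0.2, 0.3 or 0.4. Margins 0.85 and 0.90, for illustration only. With two scans per patient and no missing scans, the mixed-model contrast is taken to behave as a paired t-test on the log ratio.

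**Step 1: true ratio equal to 1.** By construction, a 0.05 test is then non-significant with probability 1 - 0.05 = 95%.

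**Step 2: largest observed loss that remains non-significant.** Loss = 1 - exp(-t(0.975, n-1) × SD / √n), with t = 2.0395 for n = 32 and 2.2622 for n = 10. For example, with n = 32 and SD 0.2: 2.0395 × 0.2 / √32 = 0.0721, and 1 - exp(-0.0721) = 7.0%.

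| SD | n = 32 | n = 10 |
|---|---|---|
| 0.2 | 7.0% | 13.3% |
| 0.3 | 10.3% | 19.3% |
| 0.4 | 13.4% | 24.9% |

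**Step 3: chance that a true 10% loss gives a non-significant result** (noncentral t, noncentrality ln(0.90) × √n / SD).

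| SD | n = 32 | n = 10 |
|---|---|---|
| 0.2 | 18% | 68% |
| 0.3 | 51% | 83% |
| 0.4 | 70% | 88% |

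**Step 4: what a non-inferiority reading would deliver.** With true ratio 1, power = P(T > t(0.975, n-1)), where T is noncentral t with noncentrality -ln(margin) × √n / SD. For margin 0.85, SD 0.3 and n = 32, the noncentrality is 0.1625 × √32 / 0.3 = 3.06 and power is 84%.

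| Margin | SD | n = 32 | n = 10 |
|---|---|---|---|
| 0.85 | 0.2 | 99% | 63% |
| 0.85 | 0.3 | 84% | 33% |
| 0.85 | 0.4 | 60% | 21% |
| 0.90 | 0.2 | 82% | 32% |
| 0.90 | 0.3 | 49% | 17% |
| 0.90 | 0.4 | 30% | 11% |

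Groups 1-3 can support a non-inferiority reading if the margin is not too tight for the actual SD. Group 4 has little power for it under most of these assumptions.

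**Step 5: multiplicity.** Three metrics in two cohorts make six comparisons. If any one could carry the claim and all were independent, the chance of at least one false positive would be 1 - 0.95^6 = 26.5%. Counting only results in favour of the grid, it would be 1 - 0.975^6 = 14.1%. Simulation with correlated metrics within a cohort gives 24% at correlation 0.5 and 19% at 0.8 in place of 26.5%.

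**The case against.** The strongest reply is that this is a single-arm pilot with cautious conclusions: Section 9.4.1 says only that improvement would indicate a potential gain. Phantom work in Section 2.2 showed CNR improved by a factor of two. A patient effect near that would be plainly significant, and the question of equivalence would not arise. This stands as a limit on severity. It does not remove the mismatch, because Section 2.1 itself says that clinical efficacy cannot be evaluated in phantoms, and Section 9.1 commits only to CNR being no worse.

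Three stronger readings are tempting, and the documents do not support them.

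- *Section 9.4.1 makes significant improvement in all three metrics a condition of success, so equal CNR fails the trial.* The sentence is interpretive. It neither requires anything nor says that every metric must improve. The mismatch with Section 9.1 is one of wording, not of two competing decision rules.
- *The plan carries a 26.5% false-positive risk.* No section says that one significant result out of six is enough. Nor are the metrics independent: Section 9.4.1 defines artifact amplitude as the range of the CT number errors in the same scan. The figure is an upper bound under a reading the plan does not state. Section 9.2 also ties the primary hypothesis to Groups 1-3, and Section 9.4.6.1 lists the proton cohort among the subgroups.
- *A CNR loss would be declared equivalent, or go unseen in Group 4.* No section says that non-significance will be read as equivalence. The per-type and subgroup intervals would let a reader see a sizeable drop in the estimates, though not the uncertainty of the paired ratio.

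**Conclusion.** The point holds for CNR. The planned difference test cannot establish the hypothesis in Section 9.1. This is a mismatch of method, not just missing detail. At two-sided 0.05, true equality gives a non-significant result 95% of the time. Observed losses of about 7-13% (n = 32) or 13-25% (n = 10) would also be non-significant if the SD of the paired log ratio lies between 0.2 and 0.4. That SD range is assumed; the documents give none.

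Alongside it, Sections 3 and 9.4.1 need aligning with Section 9.1, and the plan should say which metrics and cohort carry the primary conclusion. It would go too far to say that the primary claim cannot be decided at all: if all comparisons clearly favoured the grid, any sensible rule would agree. The gap matters when CNR is little changed or results are mixed. For a pilot, this is a should-fix.

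**What to change.** - **Section 9.4.2:** estimate the geometric-mean CNR ratio (grid over standard) from the mixed model with its 95% confidence interval. Conclude that CNR is no worse if the lower limit lies above a margin that the investigators fix and justify before analysis. Read superiority from the same interval, as a lower limit above 1.
- **Sections 3 and 9.4.1:** reword the statements on improvement so that CNR follows the hypothesis in Section 9.1.
- **Sections 9.1 and 9.4.2:** state that the primary conclusion in Groups 1-3 needs superiority on CT number error, superiority on artifact amplitude, and CNR non-inferiority. Because all three must hold, no alpha split across metrics is needed. State the significance level.
- **Group 4:** say what role its separate analysis has. With 10 participants it can give ratios with confidence intervals, but little non-inferiority power.

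The cost is wording and one margin; no further participants or scans are needed. The downside is that the joint rule is stricter than judging each metric alone, and its CNR part depends on the margin and the SD. At n = 32 and SD 0.3, moving the margin from 0.85 to 0.90 takes power from 84% to 49%. The margin should therefore be chosen on the size of CNR loss that matters for visualization, and its power stated openly.

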## 9.2 SAMPLE SIZE DETERMINATION

The sample size calculation is for the primary hypothesis. A total of 32 participants (Groups 1-3) provides non-overlapping 95% confidence intervals to detect an increase of at least 3.5% in the research CBCT ICC compared to a standard CBCT ICC of 0.95. We expect a high-level agreement for the standard CBCT method but if the ICC for the standard CBCT is slightly lower at 0.9 or even 0.8 we are still able to detect an increase in the research CBCT of at least 7.7% and 17%, respectively [34].

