For each participant and CBCT modality an average delineation will be determined using the STAPLE algorithm. This average delineation will be used as the reference delineation to compute four pairwise CIs between the reference and each observer. This pairwise approach to determine the CIs was chosen over the generalized conformity index since it can be used to account for variability among the observers, which in turn will improve our ability to compare the two imaging modalities. A two-way random effects model (random effects for participant and observer) will be carried out for each modality to calculate the ICC and its 95% confidence interval using bootstrapping for absolute agreement. The ICC will be calculated using the form ICC(2,k) so that the results can be generalized to any observer with a similar skill set. If the 95% confidence interval of ICC does not overlap between the two modalities, we will conclude they are significantly different at a 0.05 significant level. We will also examine whether anatomical location impacts performance through subgroup analyses on Groups 1-3.

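### Section 9.2 says it sizes the primary hypothesis, but every figure in it is an ICC increase, and no ICC enters the current primary analysis

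*Combined protocol and SAP*

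**What the plan says.** Section 9.2 reads: "The sample size calculation is for the primary hypothesis. A total of 32 participants (Groups 1-3) provides non-overlapping 95% confidence intervals". The effect it attaches to that number of participants is "an increase of at least 3.5% in the research CBCT ICC compared to a standard CBCT ICC of 0.95". For a standard-scan ICC of 0.9 or 0.8 it gives "an increase in the research CBCT of at least 7.7% and 17%, respectively". It states no power, number of raters, ICC form or interval formula.

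Section 9.1 defines something else: "The primary endpoint of this study is to evaluate the change in objective image quality metrics". The metrics are absolute CT number error, artifact amplitude and CNR. The first two are hypothesised to fall; CNR is hypothesised to be at least as good, with no margin. Section 9.4.2 averages each metric over its regions of interest, takes natural logs and fits a linear mixed model with a random patient effect.

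The ICC appears in two other places. Section 9.4.7 describes inter-observer ICC as one of several example exploratory analyses, to be settled after the research scans are complete. If the two modalities' 95% intervals do not overlap, "we will conclude they are significantly different at a 0.05 significant level". Section 9.4.3 names an ICC for software-versus-observer agreement, under the secondary endpoint.

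On the proton cohort, Section 9.4.1 says that "in the primary analysis, we will analyze the data from patient Groups 1-3 (TrueBeam) and Group 4 (Proteus) separately". Section 4.1 gives Group 4 10 participants.

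**The concern.** A sample-size section tells the reader what the design can resolve for its main question. This one answers a different question. The ICC increases cannot be converted into a change in CT number error, artifact amplitude or CNR, so a reader cannot tell what 32 scan pairs can show on the primary endpoint.

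This matters because the plan draws inferences. Section 9.4.1 treats a statistically significant improvement in the metrics as an indication of better visualization and accuracy. Without a stated precision, a non-significant result, above all in the 10 proton patients, could be misread as absence of effect.

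**Working it through.** **Step 1. Is the figure in 9.2 an ICC calculation?** Inputs: n=32 (9.2), k=4 observers (9.4.1), average-rater form ICC(2,k) (9.4.7). The F-based 95% interval is an assumption, because 9.2 names no formula. For an average-rater ICC r, the upper limit of the standard-scan interval equals the lower limit of the research-scan interval r1 when

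1 − r1 = (1 − r) / c, with c = F0.975(31, 93) × F0.975(93, 31) = 1.717 × 1.870 = 3.211.

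| Standard ICC | r1 = 1 − (1 − r)/3.211 | Increase r1/r − 1 | Stated in 9.2 |
|---|---|---|---|
| 0.95 | 0.9844 | 3.6% | 3.5% |
| 0.90 | 0.9689 | 7.65% | 7.7% |
| 0.80 | 0.9377 | 17.2% | 17% |

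The number of participants implied by the stated increases is 37, 32 and 34. The 0.90 and 0.80 cases agree with 32. The 0.95 case misses slightly (ICC 0.984 against 0.983), and no single variant tried reproduces all three. The source is clear enough: these are the points at which two ICC intervals stop touching. No term refers to a primary metric.

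**Step 2. Does an ICC enter the primary analysis?** Compare the sections. Sections 3, 9.1, 9.4.1 (Study #1) and 9.4.2 give three image metrics, logs, a patient random effect and a comparison of scan types, with no ICC. The rule that two ICC intervals must not overlap, which underlies 9.2, is applied to an ICC only in 9.4.7. The ICC in 9.4.3 is secondary.

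**Step 3. What does the primary analysis support?** Each participant contributes one averaged log value per metric per scan, and 9.3 requires both scans. The mixed-model contrast is then the mean within-patient log ratio, tested as a paired t with n − 1 degrees of freedom. Let SD be the standard deviation of that log ratio.

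- 95% CI half-width = t0.975(n − 1)/√n. For n=32, 2.040/5.657 = 0.36 SD. For n=10, 2.262/3.162 = 0.72 SD.
- Detectable mean difference d (in SD units) solves P[F(1, n − 1; noncentrality n·d²) > critical F] = power.

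| | n=32 | n=10 |
|---|---|---|
| 80% power, two-sided 5% | 0.51 SD | 1.00 SD |
| 90% power, two-sided 5% | 0.59 SD | 1.16 SD |
| 80% power, alpha 0.05/3 | 0.60 SD | 1.22 SD |

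The last row applies if alpha is split over the three metrics. The plan has no multiplicity rule; three independent tests at 5% would carry a familywise error of 1 − 0.95³ = 14.3%.

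**Step 4. On the ratio scale.** The documents give no SD, so 0.2, 0.4 and 0.6 are assumed. The detectable ratio at 80% power and 5% alpha is exp(−d·SD), with unrounded d of 0.511 (n=32) and 0.996 (n=10). The CI factor, by which the estimated ratio is multiplied and divided, is exp(h·SD), with h = 0.3605 and 0.7154.

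| Assumed SD | Ratio, n=32 | Ratio, n=10 | CI factor, n=32 | CI factor, n=10 |
|---|---|---|---|---|
| 0.2 | 0.90 | 0.82 | 1.07 | 1.15 |
| 0.4 | 0.82 | 0.67 | 1.16 | 1.33 |
| 0.6 | 0.74 | 0.55 | 1.24 | 1.54 |

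The ratios suit CT number error and artifact amplitude, which are hypothesised to fall. They do not size the CNR claim, which needs a margin; until one is set, the CI factor is what can be stated.

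**The case against.** This is a pilot, and a pilot need not carry a power calculation. That stands, but the protocol presents a calculation and assigns it to the primary hypothesis, so the label has to be true.

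A reader might infer that the trial is too small. The documents do not support that. The one relevant effect size they report is a two-fold CNR gain in pelvis-sized phantoms (Section 2.2). A two-fold ratio, tested at two-sided 5% with n=10, has about 99.8% power at a log-ratio SD of 0.4 and 90% at 0.6; with n=32 power is close to 100%. Phantom gains may not carry over to patients, and 10 pairs would have less power at a larger SD, but 32 may well be adequate.

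A reader might also call the 3.5% an arithmetic error. It is not shown to be one: the gap is a tenth of a percentage point, and 9.2 leaves out the inputs needed to settle it.

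On Group 4, Section 9.2 openly confines itself to Groups 1-3 and says nothing false about the proton cohort. Lastly, 9.2 does not say whose agreement its ICC measures. That it is between observers is inferred from its reference to agreement and from the matching rule in 9.4.7. The conclusion does not depend on this, because neither ICC in the plan is primary.

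**Conclusion.** Wrong as written. The only sample-size rationale in the protocol is attached to the primary hypothesis but concerns a quantity outside the primary analysis. The 3.5%, 7.7% and 17% figures therefore do not apply to the primary question. This rests on the current text alone; the amendment history, which records a move away from observer-drawn contours, only suggests how the mismatch arose.

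For the actual primary contrast, the design resolves about half an SD of the within-patient log ratio in Groups 1-3 and about one SD in Group 4, at 80% power and two-sided 5%. This assumes complete pairs and approximate normality on the log scale. Any translation into percentages depends on an SD that the documents do not supply. The missing Group 4 precision is an omission, secondary to the main point.

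**What to change.** Rewrite Section 9.2 for the current primary endpoint:

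- For CT number error and artifact amplitude, give the detectable within-patient ratio and expected 95% CI width over a stated SD range, for n=32. Say whether alpha is split over the three metrics.
- For CNR, give the expected CI width, or state a margin and size against it.
- Give the n=10 figures for Group 4 and describe that cohort as estimation.
- Move the ICC paragraph to Section 9.4.7, labelled exploratory, or delete it.

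A useful optional addition to Section 9.4.2 is to report the research/standard geometric mean ratio with its 95% CI, alongside the intervals already planned for each scan type.

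The cost is rewording. No patients or scans are added and the primary model is unchanged. The protocol would then show openly how much less precise the Group 4 comparison is.
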